#### 6.2.5.4. Clinical remission by PRO2 and Endoscopic Response

A cross tabulation will be created showing number and proportion of subjects with response at Week 58 (clinical remission and endoscopic response, clinical remission by PRO2 only, endoscopic response only, and no endoscopic response and no clinical remission by PRO2) by outcome at Week 10: clinical remission by PRO2 and endoscopic response, clinical remission by PRO2 alone, clinical endoscopic response only, and no endoscopic response and no clinical remission by PRO2). This table will be based on the Safety Analysis Set.

### 6.2.6. Analysis of the Primary Efficacy Endpoints for Japan Submission

The following analysis will be conducted as the primary analysis for evaluating the co-primary endpoints for the filgotinib 200 mg dose group in each Induction Study in order to support a Japanese marketing application.

Given the restriction in the US/Korea of only allowing dual refractory males to receive filgotinib 200 mg, there exists an inherent imbalance in each Induction Study between subjects randomized to filgotinib 200 mg and the placebo group with respect to US/Korea non-dual refractory males who will only be present in the placebo group, but not in the filgotinib 200 mg group.

Recognizing this imbalance and the theoretical potential for non-dual refractory subjects to have better disease prognosis and a higher chance of response, an analysis excluding US/Korea non-dual refractory males from the placebo group in the FAS for each Induction Study will be conducted. Similar analysis method as specified in Section 6.2.4 will be used for the treatment comparison between the filgotinib 200 mg and the placebo group on clinical remission by CDAI and endoscopic response at Week 10.

The primary analysis to support Japanese marketing application to evaluate efficacy of the filgotinib 100 mg dose group in each Induction Study will still be based on all the subjects in the FAS.

#### **6.2.7. Subgroup Analyses for the Primary and key secondary Efficacy Endpoints**

The following subgroup analyses of the primary efficacy endpoints will be performed for each individual study (Cohort A Induction, Cohort B Induction, and Maintenance).

Subgroups based on study stratification factors include:

##### **Cohort A Induction Study Stratification Factors:**

- Number of prior exposures to biologic agent as listed in [Appendix 2](#) ( $0, \geq 1$ )
- Concomitant use of oral, systemically absorbed corticosteroids at Day 1 (yes, no)
- Concomitant use of immunomodulators at Day 1 (yes, no)

##### **Cohort B Induction Study Stratification Factors:**

- Number of prior exposures to biologic agent as listed in [Appendix 2](#) ( $\leq 1, > 1$ )
- Concomitant use of oral, systemically absorbed corticosteroids at Day 1 (yes, no)
- Concomitant use of immunomodulators at Day 1 (yes, no)

##### **Cohort A and B Induction Studies Combined for Prior Exposure to Biologic Agent**

- Number of prior exposures to biologic agent as listed in [Appendix 2](#) ( $0, \geq 1$ )

### Maintenance Study Stratification Factors:

- History of exposure to a biologic agent (yes, no)
- Concomitant use of oral, systemically absorbed corticosteroids at maintenance baseline (yes, no)
- Concomitant use of immunomodulators at maintenance baseline (yes, no)

Other subgroups for each individual study include:

- Age group on the date of first dose of the study drug (< 65 years, ≥ 65 years)
- Sex at birth (female, male)
- Race (Asian, Black or African American, White, and Other)
- Geographic region (US, non-US)
- CCI [REDACTED]
- CCI [REDACTED]
- Duration of CD (years from date of diagnosed to first dosing date of Induction study drug) (< 1 year, ≥ 1 to < 3 years, ≥ 3 to < 7 years, ≥ 7 years)
- Baseline disease activity (based on Induction baseline CDAI score) (< 300, ≥ 300)
- Induction baseline SES-CD score (< 16, ≥ 16)
- Previous exposure to TNF- $\alpha$  antagonist (yes, no)
- Prior TNF- $\alpha$  antagonist failure (yes, no)
- Previous exposure to vedolizumab (yes, no)
- Prior vedolizumab failure (yes, no)
- Dual refractory (yes, no)
- The following 4 subgroups:
  - US/Korean males who are dual refractory
  - US/Korean males who are not dual refractory
  - Non-US/Korean males (US/Korea females and subjects from countries other than US and Korea) who are dual refractory
  - Non-US/Korean males who are not dual refractory

For a subject, if the value of the grouping variable cannot be determined, this subject will be excluded from the corresponding subgroup analysis. Non-stratified risk difference between treatment groups will be evaluated for each of the subgroups using Fisher's exact test. A forest plot will graphically present the non-stratified risk difference and 95% CI using normal approximation with a continuity correction on the treatment differences (filgotinib – placebo) in each co-primary endpoint for each of the subgroups.

Additional subgroup analyses for geographic region may be added based on the distribution of study enrollment prior to study unblinding.

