### **4.2. Induction Study (Cohorts A and B)**

#### **4.2.1. Inclusion Criteria**

Subjects must meet all of the following inclusion criteria to be eligible for participation in either the Cohort A or B Induction Study.

- 1) Must have the ability to understand and sign a written ICF, which must be obtained prior to initiation of study procedures
- 2) Males or non-pregnant, non-lactating females, ages 18 to 75 years, inclusive based on the date of the screening visit
- 3) Females of childbearing potential (as defined in [Appendix 7](#)) must have a negative serum pregnancy test at screening and a negative urine pregnancy test at baseline
- 4) Male subjects and female subjects of childbearing potential who engage in heterosexual intercourse must agree to use protocol specified method(s) of contraception as described in [Appendix 7](#)

- 5) Documented diagnosis of CD with a minimum disease duration of 3 months with involvement of the ileum and/or colon at a minimum, documented by the following:
  - a) Medical record documentation of, or an ileocolonoscopy (full colonoscopy with the intubation of terminal ileum) report dated  $\geq 3$  months before enrollment, which shows features consistent with CD, determined by the procedure performing physician AND
  - b) Medical record documentation of or a histopathology report showing features consistent with CD, determined by the pathologist.
- 6) Moderately or severely active CD as defined by:
  - a) CDAI total score between 220 and 450 inclusive (refer to [Appendix 4](#)), AND
  - b) PRO2 score consisting of abdominal pain  $\geq 2$  (on CDAI scale of 0 to 3) OR daily stool frequency  $\geq 4$  (refer to [Appendix 4](#)), AND
  - c) Evidence of active disease as measured by SES-CD (refer to [Appendix 5](#)) based on central reading:
    - i) Total score  $\geq 6$ , OR
    - ii) If disease is limited to the ileum and/or right colon, a combined score  $\geq 4$  in these two segments
- 7) Meet one of the following TB screening criteria:
  - a) No evidence of active or latent TB ie,
    - i) A negative QuantiFERON® TB-Gold In-Tube test (or centrally reported equivalent assay) at screening, AND
    - ii) A chest radiograph (views as per local guidelines) taken at screening or within the 3 months prior to screening (with the report or films available for investigator review) without evidence of active or latent TB infection, AND

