### **3.7. Data Handling Conventions and Transformations**

In general, age (in years) on the date of the first dose of study drug will be used for analyses and presentation in listings. If an enrolled subject was not dosed with any study drug, the randomization date will be used instead of the first dosing date of study drug. For screen failures, the date the informed consent was signed will be used for age calculation. If only birth year is collected on the eCRF, “01 July” will be used for the unknown birth day and month for the purpose of age calculation. If only birth year and month are collected, “15” will be used for the unknown birth day.

Duration of CD (years) is the number of years between the diagnosis date of CD and date of first dose of Induction study drug. The partial diagnosis date of CD (if any) will be imputed for calculation as follows:

- If day and month are missing but year is available, then the imputed day and month will be 01 Jan.
- If day is missing but the month and year are available, then the imputed day will be the first day of the month.
- Partial date will not be imputed if the year is missing.

Non-PK Data that are continuous in nature but are less than the lower limit of quantitation (LOQ) or above the upper LOQ will be imputed as follows:

- A value that is 1 unit less than the LOQ will be used for calculation of descriptive statistics if the datum is reported in the form of “< x” (where x is considered the LOQ). For example, if the values are reported as < 50 and < 5.0, values of 49 and 4.9, respectively, will be used for calculation of summary statistics. An exception to this rule is any value reported as < 1 or < 0.1, etc. For values reported as < 1 or < 0.1, a value of 0.9 or 0.09, respectively, will be used for calculation of summary statistics.
- A value that is 1 unit above the LOQ will be used for calculation of descriptive statistics if the datum is reported in the form of “> x” (where x is considered the LOQ). Values with decimal points will follow the same logic as above.
- The LOQ will be used for calculation of descriptive statistics if the datum is reported in the form of “≤ x” or “≥ x” (where x is considered the LOQ).

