### 5.2. Baseline Disease Characteristics

For the Induction Studies (Cohorts A and B) and Maintenance Study, the following baseline disease characteristics will be summarized for the Safety Analysis Sets using descriptive statistics for continuous variables, and using number and percentage of subjects for categorical variables:

- Duration of CD (years) from date of diagnosis to first dosing date of study drug
- Duration of CD (< 1 year, ≥ 1 to < 3 years, ≥ 3 to < 7 years, ≥ 7 years)

- CDAI score (Induction Studies only)
- PRO2 subscores: liquid or very soft stool subscore and abdominal pain subscore (Induction Studies only)
  - Liquid or very soft stool subscore  $\geq 4$
  - Abdominal pain subscore (0 = None, 1 = Mild, 2 = Moderate, 3 = Severe)
  - Abdominal pain subscore  $\geq 2$
  - Liquid or very soft stool subscore  $\geq 4$  and abdominal pain subscore  $\geq 2$
- Total PRO2 score (Induction Studies only)
- Total SES-CD score (Induction Studies only)
- Number of available segments with SES-CD at Induction baseline
- Location of CD based on SES-CD at Induction baseline: ileum only, colon only, ileum and colon
- Complications of CD:
  - Fistula (yes, no)
  - Stricture (yes, no)
  - Abscess (yes, no)
- History of surgeries due to CD (yes, no)
- [REDACTED] CCI [REDACTED]
- [REDACTED] CCI [REDACTED]
- CCI [REDACTED]
- CCI [REDACTED]
- CD treatment history
  - Prior use of systemic corticosteroids (yes, no)
  - Prior use of immunomodulators (yes, no)
  - Number of prior exposures to biologic agent (0, 1, 2,  $\geq 3$ ) as listed in [Appendix 2](#)

— Prior use of TNF- $\alpha$  antagonist as listed in [Appendix 2](#) (yes, no) and for subjects with prior use:

- Number of TNF- $\alpha$  antagonists used
  - 1
  - 2
  - $\geq 3$
- Worst outcome of prior use of TNF- $\alpha$  antagonist
  - Treatment failure
  - Intolerance, including both allergic and non-allergic intolerance
  - Other

— Prior use of vedolizumab (yes, no) and for subjects with prior use:

- Worst outcome of prior use of vedolizumab
  - Treatment failure
  - Intolerance, including both allergic and non-allergic intolerance
  - Other

— Prior use of both TNF- $\alpha$  antagonist and vedolizumab (yes, no)

— Prior use of ustekinumab (yes, no) and for subjects with prior use:

- Worst outcome of prior use of ustekinumab
  - Treatment failure
  - Intolerance, including both allergic and non-allergic intolerance
  - Other

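### Year-only Crohn's disease diagnosis dates are set to 1 January, so disease duration is only ever lengthened, by half a year on average, in the baseline table and the duration subgroups

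*SAP*

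**What the plan says.** SAP 3.7 defines the variable: "Duration of CD (years) is the number of years between the diagnosis date of CD and date of first dose of Induction study drug". It then completes partial diagnosis dates. Where only the year is known: "If day and month are missing but year is available, then the imputed day and month will be 01 Jan". Where year and month are known: "If day is missing but the month and year are available, then the imputed day will be the first day of the month". A date with no year is left missing.

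The preceding paragraph of SAP 3.7 treats partial birth dates differently. There, 01 July "will be used for the unknown birth day and month for the purpose of age calculation", and a missing day alone becomes the 15th.

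Duration is used in two places:

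- SAP 5.2 lists it as a baseline characteristic, both continuous ("Duration of CD (years) from date of diagnosis to first dosing date of study drug") and in four categories: "Duration of CD (< 1 year, ≥ 1 to < 3 years, ≥ 3 to < 7 years, ≥ 7 years".
- SAP 6.2.7 takes the same four categories as a subgroup factor in each of the three studies ("Duration of CD (years from date of diagnosed to first dosing date of Induction study drug"). SAP 6.6 extends the subgroup analyses to the secondary endpoints. Each subgroup receives an unstratified risk difference and a Fisher's exact test.

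Protocol 4.2.1, inclusion criterion 5, sets a floor on true duration: "Documented diagnosis of CD with a minimum disease duration of 3 months".

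Neither document gives a reason for using the earliest date, a count of partial diagnosis dates, or a sensitivity analysis of the rule.

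**The concern.** 1 January and the first of the month are the earliest dates that the record allows. The imputation error can therefore go only one way, towards an earlier diagnosis and a longer duration, and nothing offsets it. A subject diagnosed in early October of year Y, with the month not recorded, and first dosed on 10 January of year Y+1 has about 3 months of disease but is counted as having at least 1 year.

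Two outputs are exposed. The mean duration in the baseline table is biased upwards. In the subgroup analysis, the under-1-year group loses subjects to the next one. That group is the narrowest, because the 3-month entry floor leaves it 9 months wide. Mixing adjacent groups also blurs any real difference between early and later disease. A baseline descriptor or a subgroup boundary has no safe direction, so taking the earliest date is not conservative.

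**Working it through.** The plan states no figure for the size of this error, so there is none to reproduce.

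**Inputs**
- Imputation rules: SAP 3.7.
- Cut-offs of 1, 3 and 7 years: SAP 5.2 and 6.2.7.
- Minimum true duration of 3 months (0.25 year): Protocol 4.2.1, criterion 5.
- Assumptions not in the documents: diagnosis and dosing dates are spread evenly over the calendar year, and true durations are spread evenly within each category.

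**Step 1: the error.** For a year-only date, imputed duration = t + u. Here t is the true duration and u is the fraction of the diagnosis year already elapsed at diagnosis, 0 ≤ u < 1. The error is zero only for a true 1 January diagnosis. With u uniform, its mean is 0.5 year.

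**Step 2: crossing a cut.** A subject g years below a cut (g ≤ 1) moves up when u ≥ g, which has probability 1 − g. Averaged over a window of width w below the cut, this is 1 − w/2.

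**Step 3: by true category, year-only subjects**

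| True category | Share of category within 1 year below its upper cut | Average probability there | Moved up |
|---|---|---|---|
| 0.25 to <1 year | all (w = 0.75) | 1 − 0.375 = 0.625 | 62.5% |
| 1 to <3 years | 1/2 (w = 1) | 0.5 | 25% |
| 3 to <7 years | 1/4 (w = 1) | 0.5 | 12.5% |
| ≥7 years | none | – | 0% |

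No one moves down.

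**Step 4: check on calendar dates.** I simulated 3 million subjects, with dosing dates uniform over five calendar years and true duration uniform from 0.25 to 15 years. The mean error was 0.499 year and the maximum 0.999. Shares moved up were 62.5%, 25.0%, 12.5% and 0%. For year-month dates the mean error was 14.7 days and the maximum 30.

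**Step 5: dependence on even spread.** Among year-only subjects within 12 months below the 3-year cut, the share moved up depends on the dosing month: 95% for January, 79% for March, 55% for June, 29% for September and 4% for December. The 50% in the table is an average over the year.

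**Step 6: the mid-point rule.** With 1 July the error is about u − 0.5. Its simulated mean was 0.003 year, with a range of about −0.5 to +0.5.
- 3-year cut: 12.5% of those within a year below move up, and 12.3% of those within a year above move down.
- 7-year cut: 12.7% up and 12.4% down.
- 1-year cut: 16.8% of the 0.75-year band below moves up, and 12.5% of the 1-year band above moves down. Weighted by width, 0.168 × 0.75 = 0.126 against 0.125 × 1 = 0.125.

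Overall, 5.1% of simulated year-only subjects were in the wrong category, against 10.0% under the 1 January rule. About 0.2% had a negative duration, which a cap at 3 months before first dose removes. The cap acts only where the imputed duration is below 0.25 year and sets it to 0.25 year, so it moves no one across a cut.

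**The case against.** The strongest reply is that nothing inferential depends on this variable. Duration is not among the factors in the stratified tests of SAP 6.2.4 and has no place in the alpha scheme of SAP 3.5. The rule is prespecified and uses only the diagnosis date and the first dose date, so it treats all arms alike. Moving a subject to the adjacent duration group does not favour filgotinib or placebo within a group. All of this stands and limits the point to a minor one.

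Three further arguments have some force.

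- Criterion 5 requires documented disease of at least 3 months, so recent diagnoses may be the ones most likely to carry a month. Year-only dates could then be rarest where the shift is largest. The documents cannot settle this, but it is a reason not to apply the 62% to the whole under-1-year group.
- The 1 January rule never gives a negative duration and never takes an eligible subject below the 3-month floor, whereas 1 July can. That is true, and it is why the fix needs a cap.
- Birth date is a different variable, so a different rule for it is not in itself an error. Agreed: the point rests on the one-sided error. The birth-date rule shows only that the SAP already has a two-sided convention to hand.

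**Conclusion.** The point holds as a minor one. For year-only dates the rule overstates duration by 0.5 year on average. Under even spread of dates over the year and of durations within category, it moves about 62%, 25% and 12.5% of year-only subjects up from the first three categories, and none down. For year-month dates the error, about 15 days, is small. The effect is confined to the baseline duration table and the exploratory duration subgroups. It is blind to treatment arm and leaves the primary and key secondary tests unchanged.

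A reader might infer more in three ways, none of which the documents support.

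- That half or more of each duration subgroup is misfiled. The shares apply only to year-only subjects, and half or more applies only close to a cut or in the under-1-year category.
- That a definite fraction of the under-1-year subgroup is wrong. Guessing that 10–30% of dates are year-only would give 0.625 × 10–30%, or about 6–19%. But the documents give no such share, so the effect on the whole subgroup is unknown.
- That the subgroup results describe the wrong subjects or bias the treatment comparison. At most, some subjects sit in the adjacent group, irrespective of arm.

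**What to change.** In SAP 3.7, impute a year-only diagnosis date as 1 July and a year-month date as the 15th, as is already done for birth dates. If the imputed date falls later than 3 months before first dose, set it to 3 months before first dose, in line with inclusion criterion 5. Use the resulting duration in both the SAP 5.2 table and the SAP 6.2.7 subgroups.

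The cost is two lines of SAP text and one derivation, with no new data. Individual imputed values remain approximate, and some subjects near a cut will still be misfiled, but in both directions so that the shifts largely cancel.

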##### Other (non-EU)

The sample size was chosen to ensure that a clinically meaningful difference in both clinical remission rate by CDAI at Week 10 and endoscopic response rate at Week 10 could be detected when comparing filgotinib 200 mg to placebo within each Induction Study.

A sample size of 220 subjects in each treatment group (N = 660 total) will provide an overall power of 97% for a filgotinib 200 mg dose group comparison to placebo at a 2-sided 0.05 significance level to detect a treatment difference of 20% in clinical remission rate by CDAI at Week 10 (45% on filgotinib 200 mg and 25% on placebo) and a treatment difference of 15% in endoscopic response rate at Week 10 (25% on filgotinib 200 mg and 10% on placebo). Since each endpoint needs to achieve statistical significance, the overall power of 97% is calculated as the product of the two individual powers based on each endpoint.

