## 6.6. Change from Protocol-Specified Efficacy Analyses

CCI

• CCI

• CCI

• CCI

- CCI [REDACTED]
  - CCI [REDACTED]
- CCI [REDACTED]

Subgroup analyses as defined for the co-primary endpoints, were added for all secondary endpoints.

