	Appendix 7	Added appendix for determining missing and virtual visits due to COVID-19	To provide details of the determination algorithm
	Global	Administrative and editorial changes have been made throughout the SAP, where appropriate	To improve clarity and consistency
Version 1.0 (07 February 2022)	3.8.3	Added the data handling rule for shift tables in safety endpoints	To use a conservative rule for shift tables in safety endpoints
	4.1	Added key study dates table	To provide information for the clinical study report
	4.5	Added overall assessment of COVID-19 impact	To address the overall COVID-19 impact at subject level
	5.2	Added summary of each abdominal pain subscore	To better assess the baseline characteristics of the analysis population
	5.2	Added the number of available segments with SES-CD score for Maintenance study	In response to comments from FDA
	6.2.4	Added summary of the number of available segments with SES-CD score at Induction baseline and post Induction baseline, and change from Induction baseline	In response to comments from FDA
	6.2.5	Added tipping point analysis as a sensitivity analysis for the primary endpoints	To assess the robustness of analysis result under the MNAR (missing not at random) assumption.
	CCI	CCI	CCI
	Appendix 8	Added the SAS programming for the tipping point analysis for binary endpoint	To provide clear guidance on the tipping point analysis
	Global	Editorial changes or clarification languages have been provided throughout the SAP, where appropriate	To improve clarity and consistency
Version 2.0 (xx January 2022)	Global	This SAP is a combination of the SAP for submission within EU and the SAP for submission outside EU. Objectives for both regions and corresponding analyses methods are combined in this SAP	To have one SAP covering all regions
	3.4 and 6.2.7	Add subgroups for key secondary endpoints in addition to the co-primary endpoints	To further explore consistency of the results

Revision Date (DD MMM YYYY)	Section	Summary of Revision	Reason for Revision
	3.8.2	Gaps between analyses visit windows were removed by extending the windows	To make sure all data is included in the analyses
	4.2.1	Improved on the calculation of extent of exposure	To cover all possible scenarios of (partially) missing data
	4.2.2	Modified the calculation of treatment adherence + modified the treatment adherence categories	To be able to summarize overdoses

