	4.3	Removed tabulation of minor protocol deviations	Because the database will not allow this summary
	4.5 7.1.6	Remove overall assessment of COVID-19 pandemic impact Added a listing on the COVID-19 related AEs	To avoid duplication in the listings. All aspects of the removed listing were covered in other more detailed listings, except for the COVID-19 AEs, for which a listing was added in section 7.1.6
	5.2	Add additional categories for baseline prednisone equivalent dose	To better characterize baseline prednisone equivalent dose
	6.2.5.4	Added a cross-tabulation of CDAI remission and SES-CD response at Week 58 versus Week 10	Not all subjects entering the Maintenance study achieved CDAI remission. The cross-tabulation was added to explore those subjects
	6.2.7	- Added subgroup for prior exposure to biologic agents in Cohorts A and B combined - subgroup on number of prior exposure combined categories with low numbers for Cohort A	- Cohort A includes both subjects with and without prior experience to biologic agents. Cohort B only has subjects with prior exposure. Therefore, the best comparison between those with and without treatment experience is the comparison combining both Cohorts. - To avoid subgroups with very low numbers
	6.6	Updated to include all changes to protocol-specific efficacy analyses	Because the list was incomplete
	7.1.6	- Added a summary of AEs with pre-specified cut-off - added a listing for COVID-19 related AEs	- To streamline CSR writing (table with cut-off in the body of the CSR and the complete table in the CSR appendices) - to describe all aspects of the pandemic
	7.4	Change the sorting order of prior and concomitant therapies	To streamline CSR writing
	8 Appendix 10	- Description of PK analyses replaced by the PKAP in appendix 10 - Additional PK parameters were added	- To allow for a better flow of the SAP - To characterize the pharmacokinetics in more detail
	Appendix 9	Add the list of preferred terms based on the latest MedDRA version	Even though previously removed to reduce the burden of updating the list with each MedDRA up-versioning, it was decided to put the lists back in based on the latest MedDRA version.
	Global	The EU-specific SAP and the SAP for non-EU submission were combined into 1 SAP	To have 1 SAP covering all submissions

---

Revision Date (DD MMM YYYY)	Section	Summary of Revision	Reason for Revision

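### The planned within-level Fisher tests in SAP 6.2.7 do not address whether the treatment effect is consistent across subgroups, so a treatment-by-subgroup test should be added and the within-level p-values not used for that purpose

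*SAP*

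**What the plan says.** The method paragraph at the end of SAP 6.2.7 is fully visible. It states: "Non-stratified risk difference between treatment groups will be evaluated for each of the subgroups using Fisher's exact test". It then adds a display: "A forest plot will graphically present the non-stratified risk difference and 95% CI using normal approximation with a continuity correction", drawn for each co-primary endpoint and each subgroup. No significance level, multiplicity statement or reading rule is given for the subgroup p-values.

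SAP 6.6 extends the scope: "Subgroup analyses as defined for the co-primary endpoints, were added for all secondary endpoints". The revision table (SAP section 12, Version 2.0) gives the reason for adding the key secondary endpoints as "To further explore consistency of the results". SAP 6.2.7 also contains a pooled analysis headed "Cohort A and B Induction Studies Combined for Prior Exposure to Biologic Agent", with levels 0 and 1 or more prior biologics. The revision table justifies it on the ground that "the best comparison between those with and without treatment experience is the comparison combining both Cohorts".

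No treatment-by-subgroup or heterogeneity test appears in the visible text of either document.

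**The concern.** Consistency across levels, and a contrast of naive with experienced subjects, both concern the null hypothesis that the treatment difference is the same in every level. Fisher's test within a level has a different null: no difference in that level. A level can be non-significant only because it is small, and a significant level beside a non-significant one does not show that the effects differ. Equally, two significant levels do not show equal effects.

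SAP 6.2.7 lists many factors, for two doses and several endpoints, so mixed p-values are to be expected even if the drug works equally well everywhere. What is at stake is the reading of the subgroup tables. For the key secondary endpoints the Fisher p-value is the only subgroup inference explicitly named.

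**Working it through.** **Inputs from SAP 1.3.** Induction has 220 per arm. Planning rates, filgotinib 200 mg vs placebo, are CDAI remission 45% vs 25%, PRO2 remission 30% vs 15% and endoscopic response 25% vs 10%. Maintenance has 120 vs 60 subjects, with 50% vs 20% on both co-primary endpoints. The main comparison is a "comparison to placebo at a 2-sided 0.05 significance level".

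**Assumptions.** The documents give no subgroup sizes and no alpha for the subgroup tests. I assume two-sided 0.05, a range of splits, and the full planning effect in every level.

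**Step 1: reproduce the plan's power.** Exact Fisher power, multiplied over the two endpoints as the SAP does:
- Non-EU induction: 0.992 × 0.984 = 0.976 (stated 97%)
- EU induction: 0.960 × 0.984 = 0.945 (stated 93%)
- Maintenance: 0.978 × 0.978 = 0.957 (stated 94%)

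All are within 2 points of the stated figures, which are not in dispute.

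**Step 2: two levels with identical true effects.** Let A and B be the exact Fisher powers in the two levels. The levels are independent, so P(exactly one significant) = A(1−B) + B(1−A). For example, endoscopic response at 20/80 (44 and 176 per arm): 0.352 × 0.046 + 0.954 × 0.648 = 0.634.

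| Endpoint | Power in each half, 50/50 | Exactly one significant, 50/50 | Power small / large, 20/80 | Exactly one significant, 20/80 |
|---|---|---|---|---|
| CDAI | 0.852 | 0.253 | 0.426 / 0.972 | 0.570 |
| PRO2 | 0.717 | 0.406 | 0.294 / 0.908 | 0.668 |
| Endoscopic | 0.804 | 0.315 | 0.352 / 0.954 | 0.634 |
| Maintenance | 0.783 | 0.340 | 0.355 / 0.946 | 0.629 |

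At 10/90 the probability is 0.81 to 0.85.

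**Step 3: four equal levels** (disease duration has four; equal sizes are assumed). With power p per level, P(mixed verdicts) = 1 − p⁴ − (1−p)⁴. With p = 0.527, 0.384, 0.447 and 0.418 (CDAI, PRO2, endoscopic, Maintenance) this is 0.873, 0.834, 0.867 and 0.855.

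**Step 4: a test of the right null.** The Wald statistic is (d₁ − d₂)/√(v₁ + v₂), where d is the risk difference in a level and v its estimated variance. Simulated rejection rates with identical effects:

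| Split | Induction | Maintenance |
|---|---|---|
| 50/50 | about 5% | about 5.5% |
| 20/80 | about 5.5% | about 7% |
| 10/90 | about 6% | about 9% |
| 5/95 | about 8% | about 13% |

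The excess comes from tiny cells. At 5/95 the small level holds 11 per arm in Induction, and 6 filgotinib and 3 placebo subjects in Maintenance. At 11 per arm and a 10% placebo rate, there are no placebo responders in 0.9¹¹ = 31% of trials.

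**Step 5: pooled A+B** (440 per arm; assumed naive/experienced split from 150/290 to 220/220). At the full endoscopic effect, exactly one level is significant in only 3% to 9% of trials. At an assumed half effect (17.5% vs 10%, or CDAI 35% vs 25%) it is about 50%.

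**The case against.** The strongest reply is that the SAP never says how the Fisher p-values are to be read. A reader might infer that a non-significant level will be declared inconsistent, or its population said not to benefit. No passage supports that: the subgroup analyses sit outside the alpha-controlled family of SAP 3.5, and no decision hangs on them. Setting the probabilities above against a nominal 5% would also be unfair to Fisher's test, which was never meant to control that event. This stands. The point is that the only named test does not answer the stated question, not that the plan will draw a wrong conclusion.

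The forest plot is a real mitigation. With identical effects, its continuity-corrected intervals for two levels fail to overlap in only about 0.2% to 1.4% of simulated trials across these splits. Non-overlap is a conservative criterion, but the plot does not invite false claims of difference. The wording of SAP 6.6 might be read as carrying the plot over to the secondary endpoints; SAP 6.2.7 names only the co-primary endpoints, so this needs saying.

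Three further limits hold:
- The word consistency comes from the revision table, as the reason for adding key secondary endpoints, and could mean consistency across endpoints. SAP 6.2.7 states no purpose. The naive-versus-experienced purpose is clearer.
- Nothing in the documents shows which levels will be small. A reader might also infer that the pooled analysis will usually give discordant verdicts; at the planned endoscopic effect it would not, and the half effect is an assumption.
- An interaction test has low power, and its non-significance can be misread as proof of consistency.

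Some efficacy text is blacked out, so an interaction test there cannot be excluded.

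**Conclusion.** The concern holds as a mismatch between question and test. The within-level p-values cannot show consistency or a naive-versus-experienced difference. With identical effects they would disagree between two levels in about 25% to 41% of trials at a 50/50 split and 57% to 67% at 20/80. These figures rest on assumed splits, an assumed subgroup alpha of 0.05 and the full planning effect in every level.

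The documents do not support reading this as a flaw in the confirmatory analysis, or as a reason to drop the level-specific results. The weakness is greatest for the key secondary endpoints, where no plot is explicitly specified. The missing cohort stratification in the pooled analysis is minor: both cohorts plan 1:1:1 allocation and naive subjects belong in Cohort A. The restricted randomisation of US and Korean males (SAP 1.2.1) can still make allocation ratios differ between cohorts.

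**What to change.** In SAP 6.2.7:
- Keep the level-specific risk differences and 95% confidence intervals, and extend the forest plot to the key secondary endpoints.
- Add one nominal, exploratory treatment-by-subgroup test per factor, dose and endpoint, for example a Wald chi-square for homogeneity of risk differences with (levels − 1) degrees of freedom. Limit it to levels with both arms populated and a pre-specified minimum cell count. Show very small levels descriptively only, given the sizes of about 8% and 13% found at a 5% level.
- Leave US/Korean males who are not dual refractory out of the 200 mg test of the four-level factor. By SAP 1.2.1 and 6.2.6 they are not randomised to 200 mg, so the contrast does not exist.
- State that within-level p-values are not used to judge consistency, that a non-significant level does not prove absence of effect, and that a non-significant interaction does not prove consistency.
- For the pooled A+B analysis, compute each level's risk difference with the Mantel-Haenszel formula of SAP 6.2.4, using cohort as the stratum, and report the interaction for 0 vs 1 or more prior biologics.

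The cost is SAP wording and one extra statistic per factor, dose and endpoint, from data already collected. The downside is that interaction tests have low power and stay exploratory.
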